### **Safety statistical methods:**

Adverse events will be coded using the Medical Dictionary for Regulatory Activities (MedDRA) Version 22.1 or later. All AEs will be listed. Non-treatment-emergent AEs (Non-TEAEs) will be listed separately. All TEAEs, adverse drug reactions (ADRs), AEs of special interest, serious AEs, and serious ADRs will be summarized by system organ class and preferred terms for each treatment group. In Part 1, the DLTs will be listed.

Changes in vital signs, hematology, and clinical chemistry parameters from baseline to the end of the trial will be examined. Treatment-emergent changes from normal values to abnormal values in key laboratory parameters may be identified. Development of ADA will be examined. Effects on cognitive functions will be assessed by summarizing changes from baseline in performance testing results using descriptive statistics.

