#### Trial 03-133

As of 30 June 2019, the most common adverse events (AEs) ( $\geq 10\%$ ) were lymphopenia, platelet count decreased, white blood cell count decreased, neutrophil count decreased, vomiting, hemoglobin decreased, cough, headache, contusion, diarrhea, rhinorrhea, decreased appetite, pyrexia, abdominal pain, and nausea. The most common serious adverse events ( $\geq 5\%$ ) were platelet count decreased, neutrophil count decreased, and white blood cell count decreased. Less frequent, but clinically significant serious adverse events ( $< 5\%$ ) include myelodysplastic syndrome, acute myeloid leukemia, seizure, and depressed level of consciousness. 10% of patients discontinued from treatment with I-omburtamab due to adverse events, including decreased platelet count, chemical meningitis, and immune thrombocytopenic purpura. Serious infusion reactions included chemical meningitis, vomiting, pyrexia, headache, and nausea.

## Trial 101

As of 01 Jun 2020, the most common AEs ( $\geq 10\%$ ) were platelet count decreased, white blood cell count decreased, lymphocyte count decreased, neutrophil count decreased, nausea, headache and anemia, vomiting, pain, and pyrexia. The most common serious adverse reaction ( $\geq 10\%$ ) was platelet count decreased. Less frequent, but clinically significant serious AEs related to  $^{131}\text{I}$ -omburtamab administration were chemical meningitis and intracranial hemorrhage. The most common AE leading to discontinuation of  $^{131}\text{I}$ -omburtamab was platelet count decreased. Serious infusion reactions occurred in one patient (chemical meningitis).

## Selected AEs in Trials 03-133 and 101

Myelosuppression is caused by radiation-related adverse effects on the bone marrow and may result in severe and prolonged cytopenia. In Trial 03-133 and Trial 101, a total of 81.7% and 87.5%, respectively, had at least one event related to cytopenia. The most commonly reported hematopoietic cytopenia events were lymphopenia, platelet count decreased, and white blood cell count decreased.

Chemical meningitis is an inflammation of the meninges. Symptoms include fever, headache, nausea, and vomiting. Three patients experienced SAEs of chemical meningitis (2/109 and 1/24 in Trial 03-133 and Trial 101, respectively).

## Serious infusion reactions in Trials 03-133 and 101

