### 4.1. Inclusion Criteria

Patients must satisfy all of the following criteria at the Screening Visit, unless otherwise stated:

1. Histologically confirmed diagnosis of medulloblastoma.
2. SHH, Group 3, or Group 4 according to World Health Organization 2016 classification.
3. Recurrent or refractory to frontline therapy, defined as:
  - a. For Part 1 only: Recurrent (maximum of 2 recurrences) or refractory to frontline therapy. Prior frontline or second-line therapy may involve surgery, craniospinal irradiation, stereotactic radiosurgery, and multi-agent chemotherapy regimens.
  - b. For Part 2 only: Recurrent (maximum of 1 recurrence) or refractory to frontline therapy. Patients with recurrent disease must have received second-line chemotherapy for progressive disease. Prior frontline or second-line therapy may involve surgery, craniospinal irradiation, stereotactic radiosurgery, and multi-agent chemotherapy regimens.
4. Have refractory disease, focal or multifocal recurrent disease, or pure leptomeningeal disease. Cytological or radiographic remission is allowed; however, not simultaneously.
5. Performance status score of 50 to 100, both inclusive, on the Lansky [ $<16$  years] or Karnofsky [ $\geq 16$  years] scales.
6. Aged 3 to 19 years, both inclusive, at the time of the first planned dose of trial treatment.
7. Life expectancy of at least 3 months, as judged by the investigator.
8. Acceptable hematological status prior to first dosing (hematological support is allowed if administered at least 1 week before administration of Lu-DTPA-omburtamab), defined as:
  - a. Hemoglobin  $\geq 8$  g/dL
  - b. White blood cell count  $\geq 1000/\mu\text{L}$
  - c. Absolute neutrophil count  $\geq 1000/\mu\text{L}$
  - d. Platelet count  $\geq 75\ 000/\mu\text{L}$ .

9. Acceptable liver function prior to first dosing, defined as:
  - a. Alanine aminotransferase (ALT) and aspartate aminotransferase (AST)  $\leq 5 \times$  upper limit of normal (ULN)
  - b. Bilirubin  $\leq 1.5 \times$  ULN.
10. Acceptable kidney function prior to first dosing, defined as:
  - a. Estimated glomerular filtration rate (eGFR)  $>60$  mL/min/1.73 m^2, calculated by the 2009 revised Bedside Schwartz Equation ([Appendix 4](#)).
11. Written informed consent from legal guardian(s) and/or child obtained in accordance with local regulations. Pediatric patients must provide assent as required by local regulations.

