## 7.4. Adverse Events

### 7.4.1. Definition of Adverse Events

An AE is any untoward medical occurrence in a patient administered a pharmaceutical product which does not necessarily have a causal relationship with the treatment.

An AE can therefore be any unfavorable and unintended sign (including an abnormal laboratory finding), symptom, or disease temporally associated with the use of a product, whether or not considered related to the product.

An AE includes:

- A clinically significant worsening of a concomitant illness.
- A clinical laboratory AE: a clinical laboratory abnormality which is clinically significant, i.e., an abnormality that suggests a disease and/or organ toxicity and is of a severity that

requires active management. Active management includes interventional treatment or further investigations, for example change of medicine dose or more frequent follow-up due to the abnormality.

A pre-existing condition (i.e., a disorder present before the AE reporting period started and noted on the medical history/physical examination form) should not be reported as an AE unless the condition worsens, or episodes increase in frequency during the AE reporting period.

Diagnostic and therapeutic non-invasive and invasive procedures, such as surgery, should not be reported as AEs. A medical condition for which an unscheduled procedure was performed should, however, be reported if it meets the definition of an AE. For example, an acute appendicitis should be reported as the AE and not the appendectomy.

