### **8.5.3. Other Safety Assessments**

Changes in vital signs, hematology, and clinical chemistry parameters from baseline to the end of the trial will be examined. Treatment-emergent changes from normal values to abnormal values in key laboratory parameters may be identified. Development of ADA will be examined. Effects on cognitive functions will be assessed by summarizing changes from baseline in performance testing results using descriptive statistics.

Baseline is defined as the latest assessment prior to first dose.

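### The laboratory summaries in section 8.5.3 would not quantify the depth, grade and recovery of blood-count drops; baseline-by-worst-grade shift tables would.

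*Combined protocol and SAP*

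**What the plan says.** Section 8.5.3, repeated in the Synopsis under safety statistical methods, gives two laboratory summaries:

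- The first looks at how vital signs, blood counts and chemistry values differ between baseline and trial end.
- The second is optional: "Treatment-emergent changes from normal values to abnormal values in key laboratory parameters may be identified". The parameters counted as key are not named.

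It adds: "Baseline is defined as the latest assessment prior to first dose". It does not mention nadir, worst post-baseline value, CTCAE laboratory grade, grade-to-grade shift or time to recovery. Section 8.3 adds generic summary statistics and patient listings, but no visits or grades for laboratory data.

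Other parts of the plan bear on the point:

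- Section 4.1 requires "Acceptable hematological status prior to first dosing", with floors of hemoglobin 8 g/dL, WBC and ANC 1000/µL and platelets 75,000/µL. It also admits ALT and AST up to 5 × ULN and bilirubin up to 1.5 × ULN.
- Section 1.2.1, on the iodine-131 product, says: "Myelosuppression is caused by radiation-related adverse effects on the bone marrow and may result in severe and prolonged cytopenia". In its two trials, "a total of 81.7% and 87.5%, respectively, had at least one event related to cytopenia".
- Section 7.4.1 limits laboratory adverse events: "A clinical laboratory AE: a clinical laboratory abnormality which is clinically significant", and severe enough to need active management.
- Section 8.5.2 tabulates treatment-emergent adverse events by severity and relationship. Their number and severity form the Part 2 primary endpoint (section 2.2.1).

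**The concern.** Myelosuppression is the main toxicity expected from the iodine-131 experience and the mouse data. For a count that falls and recovers, the useful quantities are how low it went, what grade that was, how many patients reached each grade, and how long recovery took. Neither summary in 8.5.3 clearly delivers any of these.

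The normal-to-abnormal tally leaves out, parameter by parameter, the children with least reserve: those who enter with a count already low. The change summary, if it compares the first value with the last, removes any drop that has reversed.

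At stake is the description of marrow toxicity across repeated cycles. The plan itself treats grade and recovery as important. Section 3.1.2 lets accumulated toxicity over two cycles lower the recommended dose. Section 4.4 asks the DMC to weigh toxicities short of a DLT when judging whether five cycles are feasible. Section 5.3.1 ties cycle delay to Grade 3 or 4 myelosuppression and its decline to Grade 2 or lower.

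**Working it through.** **The plan's own safety figure.** Section 8.1 says that 24 patients give at least 90% probability of seeing an adverse event with 10% incidence. With n = 24 and p = 0.10, 1 − (1 − p)^n = 1 − 0.9^24 = 0.920. The figure is reproduced. It concerns adverse events in exposed patients and does not depend on 8.5.3.

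**One child through both summaries (hypothetical).** Platelets are 80,000/µL at baseline, 15,000/µL on Day 15 and 80,000/µL at the last sample. Entry is permitted, since 80,000 exceeds 75,000. Assume 80,000 is below the local normal range; the documents give no reference ranges.

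- Change from first to last value: 80,000 − 80,000 = 0.
- Normal-to-abnormal tally: not counted, because baseline was not normal.
- Change at each visit, if that is what is meant: 15,000 − 80,000 = −65,000/µL on Day 15. This could show as the minimum at that visit under 8.3, but it gives neither the number of patients per grade nor a recovery time.
- Baseline grade against worst post-baseline grade: counted, at the grade of 15,000/µL.

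**Is recovery by the last sample plausible?** In the mouse follow-up study (section 1.2.3), red cells and hematocrit were down at week 1 after the higher dose and recovering over weeks 2 to 5. The Part 1 EOT visit comes 5 to 6 weeks after the last dose. Section 1.2.1 also warns of prolonged cytopenia, so some drops would persist to that visit and show in the change summary. Only those that had recovered would be hidden.

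**When is the last count?** Table 8 marks hematology in the column for weeks 26, 39 and 52 and leaves weeks 78 and 104 blank. Its footnote 14 stops it at the first follow-up visit. The two differ and must be reconciled. On either reading, Part 2 has no scheduled count at weeks 78 or 104.

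**What do the other routes cover?**

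- DLTs (section 3.1.1.2) apply to the five weeks from first administration in Part 1 Cycle 1. Grade 4 anemia, thrombocytopenia or neutropenia qualifies only beyond a stated duration. Grade 3 thrombocytopenia qualifies only with bleeding.
- Adverse event tables cover all cycles and both parts. Section 7.4.5 records the most severe grade reached, so recovery does not erase a reported event. Entry to these tables rests on the clinical-significance judgement in 7.4.1, not on the measured value.
- Listings show every value but give no rates.

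The quantity left untabulated is therefore a graded laboratory drop that is neither a DLT nor reported as an adverse event.

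**What can the sampling support?** Hematology is drawn on Days 1, 8, 15, 22 and 29 in Part 1 Cycle 1; on Days 1, 8 and 15 and at EOT in Part 1 Cycle 2; and on Days 1, 15 and 29 of each Part 2 cycle. The largest gap within those Part 2 days is 15 − 1 = 29 − 15 = 14 days. For a drop of D days placed at random in a gap of G days, the chance that no sample catches it is max(0, 1 − D/G). For D = 7 this is 1 − 7/14 = 50% when G = 14, and 0 when G = 7. No choice of table recovers drops that fall between visits.

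**The case against.** The strongest reply is that the adverse event analysis, not 8.5.3, carries the safety endpoint. Events are graded at their worst and tabulated by severity. Worsening of a pre-existing condition is reportable, and active management under 7.4.1 includes further investigations and closer follow-up. A platelet count of 15,000/µL would be expected to prompt at least that, so it should appear in those tables. This stands, and it confines the gap mainly to milder or unreported drops.

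The phrase about change to the end of the trial can also mean change over the whole period. That stands too: the first weakness is partly ambiguity. The absence of late Part 2 counts even favors that reading, but the text should then say so.

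Three stronger conclusions might be inferred, and the documents do not support them:

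- *Myelosuppression could go unseen.* With an event rate of 81.7%, even five patients give 1 − 0.183^5 = 99.98% probability of at least one case, and the adverse event and DLT routes remain.
- *Children with low counts are excluded.* They drop out only of an optional tally, and only for the abnormal parameter. They stay in the Safety Analysis Set, change summaries, adverse event and DLT analyses, and listings.
- *The 92% detection probability falls.* If half of the 24 were abnormal at baseline, 1 − 0.9^12 = 71.8%. But that share is not in the documents, the loss is per parameter, and the 92% belongs to the adverse event route, which is untouched.

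Nor do sections 3.1.2 and 4.4 say that the dose or cycle decisions rely on the 8.5.3 summaries; the content of DMC packages is left to its charter.

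**Conclusion.** The point holds as a limited defect in a descriptive safety section, worth correcting because the remedy is cheap. As written, the laboratory summaries would not quantify depth, grade and recovery of count drops. The tally's blind spot follows directly from its definition and the entry criteria. The change summary's blind spot depends on a literal first-to-last reading.

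The loss is in the rate, grade and duration of laboratory-measured toxicity, chiefly low counts not reported as adverse events under 7.4.1. Its size depends on how many children enter with abnormal values and on how sites apply 7.4.1. The documents give neither, so no single figure is justified. The verdict also assumes that some permitted entry values lie outside local normal ranges.

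**What to change.** In 8.5.3 and the Synopsis, replace the optional normal-to-abnormal sentence with a commitment, using will, to shift tables of baseline against worst post-baseline CTCAE v5 grade:

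- derived from laboratory values, in all patients with a baseline value;
- overall, by cycle and by dose level;
- for hemoglobin, platelets, neutrophils, lymphocytes, WBC, ALT, AST, bilirubin and creatinine, all of which are in Appendix 1.

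For blood counts, add observed nadir and time to recovery to baseline grade or to Grade 2 or lower, the level that 5.3.1 already uses; here it serves only as an analysis definition. State that both are limited by the sampling days (Days 1, 15 and 29 of each Part 2 cycle). State whether the change summary is by visit or to a last value, and reconcile Table 8 with its footnote 14 on when hematology stops.

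The cost is analysis text and extra programming; no new samples are needed. One small downside is that grades based on ULN depend on local laboratory ranges, which must be available with the data.

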#### **7.1.6. Performance Status**

Since most if not all patients will have received prior craniospinal and/or whole-brain irradiation, late side effects for such previous therapies are difficult to distinguish from Lu-DTPA-omburtamab inflicted CNS AEs. However, to evaluate gross changes in neurological function, a performance test (Lansky [<16 years] or Karnofsky [ $\geq$ 16 years]) will be conducted at the Screening, EOT, and all Follow-up Visits in both parts of the trial.

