## 8. SAMPLE SIZE AND DATA ANALYSES

### 8.1. Determination of Sample Size

In Part 1, the chosen sample size is customary for studies of this nature and is not based on statistical considerations. It is estimated that up to 25 patients will participate in Part 1, based on 5 dose levels being recruited. Actual number of patients will depend on the number of DLTs observed.

For Part 2, a sample size of 24 patients provides at least 90% probability to detect an AE occurring in 10% of exposed patients.

The assumption is that 20 out of the 24 patients in Part 2 are evaluable. With 20 patients evaluable for response and a response rate of 25% (~ to 5 responders out of 20), the lower limit of the 95% confidence interval will be 9%.

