**Table 8: Schedule of Assessments – Part 2 (All Cycles)**

Dosing/Measurements/Evaluations	Screening	 Lu-DTPA-omburtamab Treatment Period 			EOT	Follow-up 	
		Cycles 1 through 5					
	Day -29* to -1	Day 1 of cycle	Day 15 (±1) of cycle	End-of-Cycle Visit (Day 29 [±1] of cycle)	5 to 6 weeks after last dose	26, 39, and 52 (±2) weeks post first dose	78 and 104 (±2) weeks post first dose
Informed consent 	X						
Eligibility check	X						
Demographics, height, body weight	X						
Medical, surgical, and disease history	X						
Prior/concomitant medications	X	X	X	X	X	X 	X 
Physical examination 	X						
Vital signs 	X	X	X	X	X	X	X
Performance test 	X 				X	X 	X 
MRI of the brain and spine 	X 			X 	X	X	X
Neurological examination 	X	X		X	X	X	X
Placement of an indwelling ICV access device	X 						
ICV access device patency/CSF flow assessment	X						
Premedication (oral dexamethasone/IV equivalent) 		X					
Anti-pyretic and anti-histaminergic premedication 		X					
ICV  Lu-DTPA-omburtamab treatment dose 		X					
Clinical chemistry and hematology 	X	X	X	X	X	X	
CSF for cytology  , total protein, glucose, and cell count	X 			X 	X	X	X
Blood and CSF for culture		X 					
Blood and CSF sampling for ADA	X 	X 			X		
Blood and CSF sampling for pharmacokinetics		X 					
Pregnancy testing 	X	X		X	X		
Adverse events 	X	X	X	X	X	X	X

Abbreviations: ADA = anti-drug antibody; AE = adverse event; CSF = cerebrospinal fluid; ctDNA = circulating tumor deoxyribonucleic acid; EOT = end of treatment; HSA = human serum albumin; ICF = informed consent form; ICV = intracerebroventricular; IMP = investigational medicinal product; IV = intravenous; MRI = magnetic resonance imaging; NCI = National Cancer Institute; SAE = serious adverse event.

\* A longer screening period (e.g., due to logistics, COVID-19 situations etc.) are allowed; however, eligibility evaluation must be re-confirmed. Screening period of >60 days with individual patient considerations to be discussed with the sponsor.

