 Measurements of heart rate, respiratory rate, temperature, and blood pressure. On dosing days, measurements to be taken before and 30 min after the end of the IMP infusion.

 Lansky Scale <16 years, Karnofsky Scale ≥16 years.

 To be performed within 3 weeks prior to first IMP infusion. May be performed on the first dosing day but it must be before IMP administration.

 MRI of the brain and spine will be completed before first IMP administration and at the End-of-Cycle (Day 29) Visit for Cycles 1 and 3 only (±4 days of the actual visit date), EOT Visit (preferably ±4 days of the actual visit date), and each Follow-up Visit (±2 weeks of the actual visit date). MRI can be performed on a different day to the other visit assessments, in accordance with investigational site standards.

 Will be used to evaluate safety and efficacy.

 Beginning 24 hours before Lu-DTPA-omburtamab administration, divided into twice-daily doses for a total of 3 days.

 Given 1-2 hours prior to Lu-DTPA-omburtamab administration, including oral acetaminophen/paracetamol and antihistamine (e.g., diphenhydramine).

 In accordance with [Appendix 1](#) and until the first follow-up visit.

 If CSF cytology sample is positive, it must be repeated within 4 weeks of the positive sampling.

 Cycles 1 and 3 only.

 Drawn and held for culture only if elevated body temperature after dosing suggests infection rather than expected response to ICV dosing. Samples to be taken within 6 hours after completion of Lu-DTPA-omburtamab infusion.

 The ADA samples must be drawn prior to dosing. Serum and CSF samples for ADA analyses will be drawn at baseline, at the start of Cycle 2 (predose), and after last treatment. Presence of ADA will be analyzed at a central laboratory.

 Blood and CSF samples for pharmacokinetics will be drawn in Cycles 1 and 2 only, as per [Table 5](#).

 Pregnancy testing (serum or urine) is mandatory for women of childbearing potential at screening, prior to each dose, and at the EOT Visit.

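### Section 8.5.3 and the Synopsis present a Lansky/Karnofsky performance-status summary as an assessment of cognition, which no scheduled test measures

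*Combined protocol and SAP*

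**What the plan says.** Section 8.5.3 (Other Safety Assessments) states: "Effects on cognitive functions will be assessed by summarizing changes from baseline in performance testing results using descriptive statistics". The Synopsis repeats this under its safety statistical methods. Section 8.5.3 takes baseline as the last assessment before the first dose and gives no further rule for this summary.

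The test itself is defined in Section 7.1.6 (Performance Status). It is done "to evaluate gross changes in neurological function, a performance test" being conducted at Screening, EOT and Follow-up Visits. The footnote to Table 8 identifies it as "Lansky Scale <16 years, Karnofsky Scale ≥16 years", and Tables 6 and 7 carry the same footnote. Inclusion criterion 5 uses the same two scales under the name of performance status: "Performance status score of 50 to 100, both inclusive".

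Section 7.1.6 also warns about attribution. Because most patients will have been irradiated before, "late side effects for such previous therapies are difficult to distinguish from" CNS events caused by the trial drug.

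Inclusion criterion 6 sets the age range: "Aged 3 to 19 years, both inclusive, at the time of the first planned dose of trial treatment". In Part 2 the last tests fall at "78 and 104 (±2) weeks post first dose".

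**The concern.** The analysis section gives the test a meaning that its defining section does not. Section 7.1.6 collects a performance-status score to pick up gross neurological change; Section 8.5.3 then calls the change in that score an effect on cognitive functions.

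The label matters because of the setting. Section 1.1 says that nearly all survivors of this disease have significant neurocognitive deficits and that regimens with less neurocognitive toxicity would be an advance. Section 1.3 repeats the need in the benefit-risk assessment. A table headed as cognitive effects would appear to address that need when nothing in the trial measures it.

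There is also a gap in the change-from-baseline rule. The scale depends on age, with a cut at 16 that lies inside the eligible range, and Part 2 patients are tested for up to two years. The plan does not say whether age at entry or age at each visit decides the scale, or whether scores from the two scales are pooled.

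**Working it through.** **Main point: tracing the term.** The plan attaches no figure to the cognitive analysis, so there is none to reproduce. The check is whether the performance testing named in Section 8.5.3 can be anything other than Lansky/Karnofsky, and whether another scheduled item could supply a cognitive result.

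| Place | Content | Measures cognition? |
|---|---|---|
| Section 7.1.6; footnotes to Tables 6, 7 and 8 | Performance test is Lansky or Karnofsky, by age | No; purpose given as gross neurological function |
| Section 4.1, criterion 5 | Same scales, named performance status | No |
| Tables 6, 7 and 8 (all rows) | No cognitive instrument listed | None |
| Section 7.1.5 | Neurological examination graded by CTCAE v5 | Not a cognitive test; not used in the 8.5.3 sentence |
| Section 7.1.4 | Mental status as one item of a physical examination at screening and when clinically indicated | Not a scheduled change-from-baseline measure; not used in the 8.5.3 sentence |

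The term has one possible referent, and the protocol itself describes that referent as something other than cognition.

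**Secondary point: patients who turn 16 on study.** The documents give no age distribution, so this is an illustration under stated assumptions.

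Inputs: ages 3 to 19 inclusive, i.e. 3 to under 20, a width of 17 years (Section 4.1); cut at 16 (Section 7.1.6); Part 2 testing to 104 weeks (Table 8); 24 patients in Part 2 and up to 25 in Part 1 (Section 8.1). Assumptions: uniform ages, everyone alive and tested throughout, 52.18 weeks per year.

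Share turning 16 = (follow-up in years) / (width of age range).

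- Part 2, 104 weeks: 104/52.18 = 1.99 years; 1.99/17 = 11.7%; × 24 = 2.8 patients.
- Part 2, 52 weeks (the full Part 2 analysis in Section 8.3): 1.00/17 = 5.9%; × 24 = 1.4 patients.
- Part 1, about 11 weeks (Cycle 2 dose 5 weeks after the first dose, EOT Visit up to 6 weeks later): 0.21/17 = 1.2%; × 25 = 0.3 patients.
- Both parts together: (2.8 + 0.3)/(24 + 25) = 3.1/49, about 6%.

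Sensitivity to the assumed age range, Part 2 at 104 weeks: ages 5 to under 20 give 1.99/15 = 13.3%, or 3.2 of 24; ages 3 to under 16 give 1.99/13 = 15.3%, or 3.7 of 24. Deaths and dropout lower every figure.

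**The case against.** The strongest reply is that this is one loose word in a descriptive safety summary. Cognition appears in none of the objectives or endpoints in Section 2. The sentence specifies no test, threshold or decision rule. Section 7.1.6 already limits interpretation by speaking of gross changes and conceding the attribution problem. This stands as a limit on weight, but it does not make the label correct.

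The second reply is that neurological harm has other routes into the report. The CTCAE neurological examination continues to 104 weeks in Part 2 (Table 8), nervous system disorders of Grade 3 and above are events of special interest (Section 7.4.4), and treatment-emergent events are tabulated (Section 8.5.2). That is true, so the performance score is not the only relevant signal. However, Section 8.5.3 does not base its cognitive statement on any of these. From five weeks after the last dose, Section 7.4.5 also narrows non-serious reporting mainly to related events of Grade 3 or higher, so milder late changes could be missed.

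Two stronger readings are tempting, and the documents do not support either.

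- A reader might infer that stable scores would be reported as no cognitive effect. The plan commits only to a descriptive summary; it draws no such conclusion in advance.
- A reader might infer that patients change scale at 16, so that change from baseline compares two instruments in about 12% of the trial. The documents assign a scale by age but do not say which age governs, so the supported statement is that the plan is silent. The 12% applies to Part 2 only and is a near-ceiling for the assumed age distribution. The protocol also applies one 50-to-100 entry range to both scales, and nothing in it shows that they cannot be compared.

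**Conclusion.** The sentence is wrong as written in Section 8.5.3 and in the Synopsis. A summary of Lansky/Karnofsky scores describes performance status and cannot support a statement about cognition; no other scheduled assessment fills the gap. This rests on the documents' own definitions and needs no numerical assumption.

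The reach is narrow: the labelling and interpretation of one safety summary. The Part 2 primary endpoint (number and severity of treatment-emergent events), the DLT evaluation, the dose recommendation and the efficacy analyses are untouched. The correction is still worth making, because neurocognitive toxicity is part of the stated unmet need and a table carrying the cognitive label would be read in that light.

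The silence on patients who turn 16 is secondary. With uniform ages from 3 to under 20 and complete follow-up it concerns about 3 of 24 Part 2 patients by 104 weeks and about 1.4 by 52 weeks. Narrower assumed age ranges raise the 104-week figure to between 3.2 and 3.7. Real follow-up would be shorter and the numbers lower.

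**What to change.** 1. In Section 8.5.3 and in the Synopsis, replace the sentence with: *Changes from baseline in performance status (Lansky/Karnofsky) will be summarized using descriptive statistics.* Delete the claim about cognitive functions.
2. Add one sentence on the age rule: either a patient keeps the baseline scale throughout, or change from baseline is computed only between scores on the same scale. List any patients who switch. Both choices are defensible. Keeping the baseline scale preserves every visit but needs a clarification of the age footnotes in Tables 6 to 8. Restricting to the same scale leaves those footnotes alone but gives no change value for visits after a switch.

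The cost is a few sentences, with no new visit, test or patient burden. The real price is that the report can no longer claim a cognitive assessment. Relabelling does not make cognition measured: if the sponsor wants such a result, an age-appropriate cognitive measure with scheduled timepoints would have to be added. Even then, with no control group and with prior irradiation, change could not be attributed to the drug from a before-and-after summary alone.
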